### **7.2 Assessing and Recording Adverse Events**

An adverse event is defined as any untoward medical occurrence in a patient or clinical investigation subject administered a pharmaceutical product and which does not necessarily have to have a causal relationship with this treatment. An adverse event can therefore be any unfavorable and unintended sign (including an abnormal laboratory finding, for example), symptom, or disease temporally associated with the use of a medicinal product or protocol-specified procedure, whether or not considered related to the medicinal product or protocol-specified procedure. Any worsening (i.e., any clinically significant adverse change in frequency and/or intensity) of a preexisting condition that is temporally associated with the use of the Merck's product, is also an adverse event.

Changes resulting from normal growth and development that do not vary significantly in frequency or severity from expected levels are not to be considered adverse events. Examples of this may include, but are not limited to, teething, typical crying in infants and children and onset of menses or menopause occurring at a physiologically appropriate time.

Merck product includes any pharmaceutical product, biological product, device, diagnostic agent or protocol-specified procedure, whether investigational (including placebo or active comparator medication) or marketed, manufactured by, licensed by, provided by or distributed by Merck for human use.

Adverse events may occur during the course of the use of Merck product in clinical trials, or as prescribed in clinical practice, from overdose (whether accidental or intentional), from abuse and from withdrawal.

Progression of the cancer under study is not considered an adverse event.

All adverse events that occur **after subject eligibility is confirmed** but before treatment allocation/randomization must be reported by the investigator if they ultimately cause the subject to be excluded from initiating treatment on the trial, or are the result of a protocol-specified intervention,

including but not limited to washout or discontinuation of usual therapy, diet, placebo treatment or a procedure.

From the time of treatment allocation/randomization through 30 days following cessation of treatment, **all non-hematologic grade  $\geq$  III adverse events must be reported by the investigator. Investigators will monitor patients carefully for early evidence of transplant-related complications, such as hyperacute graft-versus-host disease (GVHD), severe acute GVHD, steroid-requiring febrile syndrome, hepatic veno-occlusive disease, and other immune-mediated adverse reactions.** Such events will be recorded at each examination on the Adverse Event case report forms/worksheets. The reporting timeframe for adverse events meeting any serious criteria is described in section 7.2.3.1. The investigator will make every attempt to follow all subjects with non-serious adverse events for outcome.

Adverse events will not be collected for subjects during the pre-screening period (for determination of archival tissue status) as long as that subject has not undergone any protocol-specified procedure or intervention. If the subject requires a blood draw, fresh tumor biopsy etc., the subject is first required to provide consent to the main study and AEs will be captured according to guidelines for standard AE reporting.

### **7.2.1 Definition of an Overdose for This Protocol and Reporting of Overdose to the Sponsor and to Merck**

For purposes of this trial, an overdose of pembrolizumab will be defined as any dose of 1,000 mg or greater ( $\geq$ 5 times the indicated dose). No specific information is available on the treatment of overdose of pembrolizumab. Appropriate supportive treatment should be provided if clinically indicated. In the event of overdose, the subject should be observed closely for signs of toxicity. Appropriate supportive treatment should be provided if clinically indicated.

If an adverse event(s) is associated with (“results from”) the overdose of a Merck product, the adverse event(s) is reported as a serious adverse event, even if no other seriousness criteria are met.

If a dose of Merck’s product meeting the protocol definition of overdose is taken without any associated clinical symptoms or abnormal laboratory results, the overdose is reported as a non-serious Event of Clinical Interest (ECI), using the terminology “accidental or intentional overdose without adverse effect.”

All reports of overdose with and without an adverse event must be reported within 24 hours to the Sponsor and within 2 working days hours to Merck Global Safety. (Attn: Worldwide Product Safety; [contact])

### **7.2.2 Reporting of Pregnancy and Lactation to the Sponsor and to Merck**

Although pregnancy and lactation are not considered adverse events, it is the responsibility of investigators or their designees to report any pregnancy or lactation in a subject (spontaneously reported to them) that occurs during the trial.

Pregnancies and lactations that occur after the consent form is signed but before treatment allocation/randomization must be reported by the investigator if they cause the subject to be excluded from the trial, or are the result of a protocol-specified intervention, including but not limited to washout or discontinuation of usual therapy, diet, placebo treatment or a procedure.

Pregnancies and lactations that occur from the time of treatment allocation/randomization through 120 days following cessation of Sponsor’s product, or 30 days following cessation of treatment if the subject

initiates new anticancer therapy, whichever is earlier, must be reported by the investigator. All reported pregnancies must be followed to the completion/termination of the pregnancy. Pregnancy outcomes of spontaneous abortion, missed abortion, benign hydatidiform mole, blighted ovum, fetal death, intrauterine death, miscarriage and stillbirth must be reported as serious events (Important Medical Events). If the pregnancy continues to term, the outcome (health of infant) must also be reported.

Such events must be reported within 24 hours to the Sponsor and within 2 working days to Merck Global Safety. (Attn: Worldwide Product Safety; [contact])

### 7.2.3 Immediate Reporting of Adverse Events to the Sponsor and to Merck

#### 7.2.3.1 Serious Adverse Events

A serious adverse event is any adverse event occurring at any dose or during any use of Merck's product that:

- Results in death;
- Is life threatening;
- Results in persistent or significant disability/incapacity;
- Results in or prolongs an existing inpatient hospitalization;
- Is a congenital anomaly/birth defect;
- Is an other important medical event
- **Note:** In addition to the above criteria, adverse events meeting either of the below criteria, although not serious per ICH definition, are reportable to the Merck in the same timeframe as SAEs to meet certain local requirements. Therefore, these events are considered serious by Merck for collection purposes.
  - Is a new cancer (that is not a condition of the study);
  - Is associated with an overdose.

Refer to Table 6 for additional details regarding each of the above criteria. For the time period beginning when the subject is enrolled until treatment is initiated, any serious adverse event, or follow up to a serious adverse event, including death due to any cause other than progression of the cancer under study (reference Section 7.2.3.3 for additional details) that occurs to any subject must be reported within 24 hours to the Sponsor and within 2 working days to Merck Global Safety if it causes the subject to be excluded from the trial, or is the result of a protocol-specified intervention, including but not limited to washout or discontinuation of usual therapy, diet, placebo treatment or a procedure.

NOTE: for the purposes of this protocol planned hospitalizations solely for administration of protocol-specified chemotherapy for tumor progression will not require expedited reporting. For the time period beginning at treatment allocation/randomization through 30 days following cessation of treatment, any serious adverse event, or follow up to a serious adverse event, including death due to any cause other than progression of the cancer under study (reference Section 7.2.3.3 for additional details), whether or not related to the Merck product, must be reported within 24 hours to the Sponsor and within 2 working days to Merck Global Safety.

Additionally, any serious adverse event, considered by an investigator who is a qualified physician to be related to Merck product that is brought to the attention of the investigator at any time following consent through the end of the specified safety follow-up period specified in the paragraph above, or at any time outside of the time period specified in the previous paragraph also must be reported immediately to the Sponsor and to Merck Global Safety.

All subjects with serious adverse events must be followed up for outcome.

**SAE reports and any other relevant safety information are to be forwarded to the Merck Global Safety [contact]**

A copy of all 15 Day Reports and Annual Progress Reports is submitted as required by FDA, European Union (EU), Pharmaceutical and Medical Devices agency (PMDA) or other local regulators. Investigators will cross reference this submission according to local regulations to the Merck Investigational Compound Number (IND, CSA, etc.) at the time of submission. Additionally investigators will submit a copy of these reports to Merck & Co., Inc. (Attn: Worldwide Product Safety; [contact]) at the time of submission to FDA.

#### **7.2.3.2 Events of Clinical Interest**

Selected non-serious and serious adverse events are also known as Events of Clinical Interest (ECI) and must be reported within 24 hours to the Sponsor and within 2 working days to Merck Global Safety. (Attn: Worldwide Product Safety; [contact]).

For the time period beginning when the consent form is signed until treatment allocation/randomization, any ECI, or follow up to an ECI, that occurs to any subject must be reported within 24 hours to the Sponsor and within 2 working days to Merck Global Safety if it causes the subject to be excluded from the trial, or is the result of a protocol-specified intervention, including but not limited to washout or discontinuation of usual therapy, diet, placebo treatment or a procedure.

For the time period beginning at treatment allocation/randomization through 90 days following cessation of treatment, or 30 days following cessation of treatment if the subject initiates new anticancer therapy, whichever is earlier, any ECI, or follow up to an ECI, whether or not related to Merck product, must be reported within 24 hours to the Sponsor and within 24 hours to Merck Global Safety.

Events of clinical interest for this trial include:

1. an overdose of Merck product, as defined in Section 7.2.1 - Definition of an Overdose for This Protocol and Reporting of Overdose to the Sponsor, that is not associated with clinical symptoms or abnormal laboratory results.
2. When **NOT** deemed to be related to underlying leukemia, an elevated AST or ALT lab value that is **greater than or equal to 5X** the upper limit of normal and an elevated total bilirubin lab value that is greater than or equal to 2X the upper limit of normal and, at the same time, an alkaline phosphatase lab value that is less than 2X the upper limit of normal, as determined by way of protocol-specified laboratory testing or unscheduled laboratory testing.\*

**\*Note:** These criteria are based upon available regulatory guidance documents. The purpose of the criteria is to specify a threshold of abnormal hepatic tests that may require an additional evaluation for an underlying etiology.

#### **7.2.4 Evaluating Adverse Events**

An investigator who is a qualified physician will evaluate all adverse events according to the NCI Common Terminology for Adverse Events (CTCAE), version 4.0. Any adverse event which changes CTCAE grade

over the course of a given episode will have each change of grade recorded on the adverse event case report forms/worksheets.

All adverse events regardless of CTCAE grade must also be evaluated for seriousness.

**Table 6 Evaluating Adverse Events**

An investigator who is a qualified physician, will evaluate all adverse events as to:

V4.0 CTCAE Grading	Grade 1	Mild; asymptomatic or mild symptoms; clinical or diagnostic observations only; intervention not indicated.
	Grade 2	Moderate; minimal, local or noninvasive intervention indicated; limiting age-appropriate instrumental ADL.
	Grade 3	Severe or medically significant but not immediately life-threatening; hospitalization or prolongation or hospitalization indicated; disabling; limiting self-care ADL.
	Grade 4	Life threatening consequences; urgent intervention indicated.
	Grade 5	Death related to AE
Seriousness	A serious adverse event is any adverse event occurring at any dose or during any use of Merck product that:	
	† Results in death ; or	
	† Is life threatening ; or places the subject, in the view of the investigator, at immediate risk of death from the event as it occurred (Note: This does not include an adverse event that, had it occurred in a more severe form, might have caused death.); or	
	† Results in a persistent or significant disability/incapacity (substantial disruption of one's ability to conduct normal life functions); or	
	† Results in or prolongs an existing inpatient hospitalization (hospitalization is defined as an inpatient admission, regardless of length of stay, even if the hospitalization is a precautionary measure for continued observation. (Note: Hospitalization for an elective procedure to treat a pre-existing condition that has not worsened is not a serious adverse event. A pre-existing condition is a clinical condition that is diagnosed prior to the use of a Merck product and is documented in the patient's medical history.); or	
	† Is a congenital anomaly/birth defect (in offspring of subject taking the product regardless of time to diagnosis); or	

	
Is a new cancer (that is not a condition of the study) (although not serious per ICH definition, is reportable to the Sponsor within 24 hours and to Merck within 2 working days to meet certain local requirements); or
 
Is an overdose (whether accidental or intentional). Any adverse event associated with an overdose is considered a serious adverse event for collection purposes. An overdose that is not associated with an adverse event is considered a non-serious event of clinical interest and must be reported within 24 hours to the Sponsor and to Merck within 2 working days..
 
Other important medical events that may not result in death, not be life threatening, or not require hospitalization may be considered a serious adverse event when, based upon appropriate medical judgment, the event may jeopardize the subject and may require medical or surgical intervention to prevent one of the outcomes listed previously (designated above by a †).

Duration	Record the start and stop dates of the adverse event. If less than 1 day, indicate the appropriate length of time and units
Action taken	Did the adverse event cause Merck product to be discontinued?
Relationship to Merck Product	
Did Merck product cause the adverse event? The determination of the likelihood that Merck product caused the adverse event will be provided by an investigator who is a qualified physician. The investigator's signed/dated initials on the source document or worksheet that supports the causality noted on the AE form, ensures that a medically qualified assessment of causality was done. This initialed document must be retained for the required regulatory time frame. The criteria below are intended as reference guidelines to assist the investigator in assessing the likelihood of a relationship between the test drug and the adverse event based upon the available information.
 
The following components are to be used to assess the relationship between Merck product and the AE; the greater the correlation with the components and their respective elements (in number and/or intensity), the more likely Merck product caused the adverse event (AE):

Exposure	Is there evidence that the subject was actually exposed to Merck product such as: reliable history, acceptable compliance assessment (pill count, diary, etc.), expected pharmacologic effect, or measurement of drug/metabolite in bodily specimen?

Time Course	Did the AE follow in a reasonable temporal sequence from administration of Merck product? Is the time of onset of the AE compatible with a drug-induced effect (applies to trials with investigational medicinal product)?
Likely Cause	Is the AE not reasonably explained by another etiology such as underlying disease, other drug(s)/vaccine(s), or other host or environmental factors

Relationship to Merck Product (continued)	The following components are to be used to assess the relationship between the test drug and the AE: (continued)	
	Dechallenge	Was Merck product discontinued or dose/exposure/frequency reduced?  If yes, did the AE resolve or improve?  If yes, this is a positive dechallenge. If no, this is a negative dechallenge.  (Note: This criterion is not applicable if: (1) the AE resulted in death or permanent disability; (2) the AE resolved/improved despite continuation of the Sponsor's product; or (3) the trial is a single-dose drug trial); or (4) Sponsor's product(s) is/are only used one time.)
	Rechallenge	Was the subject re-exposed to Merck product in this study?  If yes, did the AE recur or worsen?  If yes, this is a positive rechallenge. If no, this is a negative rechallenge.  (Note: This criterion is not applicable if: (1) the initial AE resulted in death or permanent disability, or (2) the trial is a single-dose drug trial); or (3) Sponsor's product(s) is/are used only one time).  NOTE: IF A RECHALLENGE IS PLANNED FOR AN ADVERSE EVENT WHICH WAS SERIOUS AND WHICH MAY HAVE BEEN CAUSED BY MERCK PRODUCT, OR IF REEXPOSURE TO MERCK PRODUCT POSES ADDITIONAL POTENTIAL SIGNIFICANT RISK TO THE SUBJECT, THEN THE RECHALLENGE MUST BE APPROVED IN ADVANCE BY THE SPONSOR AS PER DOSE MODIFICATION GUIDELINES IN THE PROTOCOL.
	Consistency with Trial Treatment Profile	Is the clinical/pathological presentation of the AE consistent with previous knowledge regarding Merck product or drug class pharmacology or toxicology?
The assessment of relationship will be reported on the case report forms /worksheets by an investigator who is a qualified physician according to his/her best clinical judgment, including consideration of the above elements.		

Record one of the following	Use the following scale of criteria as guidance (not all criteria must be present to be indicative of Merck product relationship).
Yes, there is a reasonable possibility of Merck product relationship.	There is evidence of exposure to Merck product. The temporal sequence of the AE onset relative to the administration of Merck product is reasonable. The AE is more likely explained by Merck product than by another cause.
No, there is not a reasonable possibility of Merck product relationship	Subject did not receive the Merck product OR temporal sequence of the AE onset relative to administration of Merck product is not reasonable OR the AE is more likely explained by another cause than the Merck product. (Also entered for a subject with overdose without an associated AE.)

### **7.2.5 Sponsor Responsibility for Reporting Adverse Events**

All Adverse Events will be reported to regulatory authorities, IRB/IECs and investigators in accordance with all applicable global laws and regulations.

## **8.0 STATISTICAL ANALYSIS PLAN**

### **8.1 Statistical Analysis Plan Summary**

The statistical plan for this feasibility study of pembrolizumab for relapse after HCT is primarily directed toward the primary objective of safety and feasibility after HCT. The trial will additionally estimate the proportion of patients responding to pembrolizumab monotherapy by overall response rate (ORR). The ORR (CR+PR) will also be estimated at day 35 and 77 for subjects receiving  $\geq$  one dose of single agent pembrolizumab. If progression is noted subjects may receive standard induction chemotherapy. Subjects who are administered standard induction chemotherapy prior to day 77 (for any reason) will be considered non-responders for ORR of pembrolizumab monotherapy. However, we will perform a planned subset analysis to determine the ORR at day 77 for subjects receiving pembrolizumab followed by systemic chemotherapy.

The incidence of grade 3-4 acute GvHD and significant ( $\geq$  grade 3) immune mediated toxicities will be estimated at the conclusion of the treatment period which is 30 days after the last dose of pembrolizumab. Overall survival (OS) and Disease Free Survival (DFS) at 12 months will be calculated by Kaplan Meier methods. The observation period for OS and DFS will begin at the confirmed date of relapse after HCT until death or last scheduled clinical follow up. These observations will assist in determining whether further investigations are warranted after HCT.

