### 2.2 Trial Diagram

\* standard induction chemotherapy may be administered during induction at investigators discretion if concern for rapid clinical progression of malignancy (see 5.2.1.2).

† Primary study endpoint (s) are ORR (PR+CR) at day 35 and day 77

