#### **4.2.2 Rationale for Endpoints**

##### **4.2.2.1 Efficacy Endpoints**

This feasibility study addresses a cohort of patients with established resistance to chemotherapy and HCT by virtue of having relapsed after HCT. We are seeking to identify a signal for clinical benefit by assessing the ORR to pembrolizumab  $\pm$  chemotherapy while providing additional insights into the mechanisms of check-point inhibition in the immune biology of post-HCT relapse. These efficacy endpoints will be assessed by serial CBC, bone marrow biopsies / aspirate, assessing peripheral blast percentages, absolute blast counts (ABC), and marrow blasts.

The time to response in this disease cohort is unknown. The first marrow assessment of disease response will be at day 35 after initiation of study treatment. If disease is stable (SD) or improved (CR or PR) at day 35, clinicians will continue single agent therapy every 3 weeks for a total of 4 doses. A second marrow assessment will be performed on day 77. If CR or PR is attained subjects may proceed to phase II (maintenance) (see section 5.2).

If there is a concern for rapid disease progression or clinical instability, chemotherapy may be added per investigators discretion after the day 35 marrow results (two doses of pembrolizumab) (See section 5.2.1.2).. Subjects may continue study drug in the absence of toxicity attributable to pembrolizumab per Table 3.

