#### **Primary objective endpoints:**

Efficacy:

- ORR at days 35 and 77 in subjects receiving pembrolizumab monotherapy
- ORR at day 77 in subjects receiving pembrolizumab  $\pm$  standard induction chemotherapy
- Clinical Benefit Rate (CBR) at days 35 and 77 in subjects receiving pembrolizumab monotherapy

Safety:

- Incidence and severity of GvHD after administration of pembrolizumab
- Grade 3-5 Regimen-related toxicities (RRT) per CTCAE v4
- Incidence of immune mediated toxicities attributable to pembrolizumab

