### 8.2.2 Sample size estimate to assess if study drug is promising for further study

Considering the highly refractory nature of the subjects to be enrolled in this study and our lack of understanding of the kinetics of response to pembrolizumab in the post HCT setting, the investigators will be cautious about the potential underestimation of response of this novel agent. In addition, several, but not all patients are expected to receive standard chemotherapy at some point during their on-study therapy, thereby potentially confounding interpretation of the response rate to study drug. Therefore, the following criteria will be used to assess if the study drug is promising for further study:

(a) if  $\geq 4$  subjects demonstrate evidence of clinical benefit the drug will be considered promising. With 20 subjects we would be 90% confident that the true clinical benefit rate (CBR) lies between 7% and 40%. The CBR will be assessed on both day 35 and day 77 as determined by the proportion of subjects who receive pembrolizumab monotherapy who achieve either stable disease (SD) or ORR prior to the addition of standard chemotherapy

(b) the observation of any CRs seen in subjects not receiving standard chemotherapy will be considered promising.

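### The Section 8.1 chemotherapy rule names no assessment date, so chemotherapy started after day 35 can turn a documented day-35 monotherapy response into a non-response

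*Combined protocol and SAP*

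**What the plan says.** Monotherapy ORR at both dates is a primary efficacy endpoint. Section 4.2.2.1 lists "ORR at days 35 and 77 in subjects receiving pembrolizumab monotherapy", Section 8.2.1 repeats it, and the note to the diagram in Section 2.2 reads "Primary study endpoint (s) are ORR (PR+CR) at day 35 and day 77".

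Section 8.1 says that ORR "will also be estimated at day 35 and 77 for subjects receiving" at least one dose of single-agent pembrolizumab. Two sentences later it gives the rule at issue: "Subjects who are administered standard induction chemotherapy prior to day 77 (for any reason) will be considered non-responders for ORR of pembrolizumab monotherapy". The sentence after that provides a separate day-77 ORR for subjects who received pembrolizumab and then chemotherapy.

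Section 8.2.2 sets two criteria for calling the drug promising. Criterion (a) needs at least 4 subjects with clinical benefit, judged on days 35 and 77, and counts those on monotherapy "who achieve either stable disease (SD) or ORR prior to the addition of standard chemotherapy". Criterion (b) is that "the observation of any CRs seen in subjects not receiving standard chemotherapy will be considered promising". The same section warns that "the investigators will be cautious about the potential underestimation of response of this novel agent".

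On treatment, Section 4.2.2.1 keeps subjects with SD, PR or CR at day 35 on single agent. It also says that, if rapid progression or instability is a concern, "chemotherapy may be added per investigators discretion after the day 35 marrow results". Section 5.2.1.2 likewise allows chemotherapy at the physician's discretion for impending rapid relapse.

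**The concern.** A response at day 35 is a fact about the day-35 marrow. Under the Section 8.1 wording, whether it counts depends on what happens over the following six weeks. A subject in PR on day 35 who starts chemotherapy on, say, day 60 becomes a day-35 non-responder. A second subject with the same day-35 marrow who loses the response but is not given chemotherapy keeps the day-35 response. The score then reflects a discretionary treatment decision rather than the marrow.

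Section 5.2.1.2 discourages chemotherapy before the day-35 marrow, so day-35 ORR is the reading of pembrolizumab activity least mixed with chemotherapy. An error in it that runs only downward is also the kind that Section 8.2.2 says the investigators want to guard against. Criterion (b) has a threshold of a single CR and its wording carries no time limit, so one record could decide it.

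**Working it through.** **1. The plan's own figure.** Section 8.2.2 gives a 90% interval of 7% to 40% with 20 subjects. The exact (Clopper-Pearson) interval for 4 of 20 is Beta(0.05; 4, 17) to Beta(0.95; 5, 16) = 7.1% to 40.1%. This reproduces the figure, and the point made here does not affect it. The plan states no figure for ORR or for the effect of the chemotherapy rule.

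**2. One subject under each rule.** Take a subject with PR on the day-35 marrow, no chemotherapy before it, and chemotherapy from day 60 (day 60 is illustrative).

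| Quantity | Governing text | Score |
|---|---|---|
| Day-35 CBR | 8.2.2(a): response before chemotherapy counts | benefit |
| Day-35 monotherapy ORR | 8.1 as written: chemotherapy before day 77 | non-response |
| Day-77 monotherapy ORR | 8.1 | non-response |
| Day-77 ORR with or without chemotherapy | 8.1, 8.2.1 | by the day-77 marrow |

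CBR is SD plus ORR. In the first two rows the same marrow on the same date therefore counts as a response within CBR and as a non-response in ORR.

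**3. Size per subject.** With 20 analysed, each affected subject moves day-35 ORR by 1/20 = 5 points, always downward. For example, 4/20 = 20% (exact 90% CI 7.1% to 40.1%) becomes 3/20 = 15% (4.2% to 34.4%).

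**4. Size over the trial, under assumptions.** Let r be the true day-35 ORR and q the share of day-35 responders who start chemotherapy before day 77. The documents give neither. I take r = 10% to 30% and q = 0 to 50%, with subjects independent.

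- Expected recorded day-35 ORR = r(1 − q).
- Chance that at least one of 20 is reclassified = 1 − (1 − rq)^20.

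| r | q = 10% | q = 25% | q = 50% |
|---|---|---|---|
| 10% | 9.0%; 18% | 7.5%; 40% | 5.0%; 64% |
| 20% | 18.0%; 33% | 15.0%; 64% | 10.0%; 88% |
| 30% | 27.0%; 46% | 22.5%; 79% | 15.0%; 96% |

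Each cell gives the expected recorded ORR, then the chance of at least one reclassification. Worked cell: r = 20%, q = 25% gives 0.20 × 0.75 = 15% and 1 − 0.95^20 = 64%. At q = 0 the two ways of scoring agree exactly.

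**5. Criterion (b), read literally.** Let c be the true rate of CR reached before chemotherapy, and let q now be the share of those subjects given chemotherapy at any later time. Both are again assumptions. The chance that at least one CR still counts is 1 − (1 − c(1 − q))^20.

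| c | q = 0 | q = 10% | q = 25% | q = 50% |
|---|---|---|---|---|
| 5% | 64% | 60% | 53% | 40% |
| 10% | 88% | 85% | 79% | 64% |

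**The case against.** The strongest reply is that the rule was meant for day 77 only. Its cut-off is day 77, and the next sentence supplies the matching day-77 ORR for subjects who went on to chemotherapy. Read as a pair, they give a conservative and reasonable scoring of day 77, with no conflict with 8.2.2(a). That reading is plausible. But the text does not say it: the rule is attached to monotherapy ORR, which the same paragraph has just placed at both dates, while the following sentence does name its date.

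A reader might also infer that day-35 ORR is understated. The documents do not support that. Most chemotherapy is expected after progression, and a subject who has progressed by day 35 is a day-35 non-responder under either scoring. Only a day-35 responder who starts chemotherapy before day 77 is affected. Section 4.2.2.1 keeps responders on single agent by default. Section 8.2.2 expects several subjects to receive chemotherapy but gives no rate for responders. What stands is that ORR could be understated, by an amount that may be nil.

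Nor can one infer that the promising/not promising decision would be reversed. That decision uses CBR and any CR, not ORR. An affected subject still counts toward criterion (a). Criterion (b) can also be read as no chemotherapy at the time the CR is seen; on the literal reading it changes only if the lost CR is the sole qualifying one.

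Finally, the analysis is descriptive, and no test, ORR threshold or sample size rests on the rule. That is a fair limit on severity. It does not remove the inconsistency between 8.1 and 8.2.2(a).

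**Conclusion.** The point holds as an error of wording with modest consequences. As written, Section 8.1 lets an event after day 35 overwrite a chemotherapy-free day-35 response in a listed primary endpoint, in conflict with the time-ordered rule in 8.2.2(a). The effect runs in one direction only and is 5 points per affected subject if 20 are analysed. How many subjects would be affected is unknown; the ranges shown rest entirely on assumed r, q and c, and zero is possible. Criterion (b) shares the flaw on its literal reading, with a consequence only when a single CR decides it. The documents support neither a claim of established bias nor a claim that the trial's conclusion is in danger. It is still worth settling before responses are known: in an open-label trial of 20, choosing the reading afterwards would be a post-hoc decision.

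**What to change.** In Section 8.1, replace the rule with: *A subject who starts standard induction chemotherapy before a response assessment is a non-responder for monotherapy ORR at that and all later assessments; assessments made before chemotherapy started stand as recorded.*

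In Section 8.2.2(b), refer to *any CR documented before the start of standard chemotherapy*.

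Day-77 monotherapy status for these subjects stays non-response, and the separate day-77 ORR with chemotherapy is unchanged. The trigger should stay at standard induction chemotherapy. Widening it to any new anti-leukemic therapy could make non-responders of subjects on hydroxyurea or resumed FLT-3 or tyrosine kinase inhibitors, which Section 5.3.1 permits.

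The cost is two sentences of plan text. It needs only the dates of marrow assessments and of the start of chemotherapy, with no new procedures and no change to treatment. If day 77 only was always intended, the change simply records that.
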